11.2 Prior and Concomitant Medications

Prior and concomitant medications will be coded using World Health Organization (WHO) Drug Dictionary (WHODrug Global B3 March 2020) and summarized to the therapeutic drug class (Anatomical Therapeutic Chemical [ATC] 4 classification) and preferred name (generic drug name). If the ATC 4 classification is not provided, the next lowest classification that is provided in the coding dictionary will be employed. The preferred name will be defined as the active ingredient; if the active ingredient is not provided or includes more than two ingredients (e.g., multivitamins) then the drug name will be summarized as the preferred name. Any uncoded terms will be summarized under the ATC classification of "Uncoded," but the missing preferred term will be replaced by the verbatim term entered in the eCRF.

Concomitant medications are defined as those medications listed as having been taken (1) prior to initiation of study drug administration and continuing for any period of time following the first administration of study drug or (2) at any time following the first administration of study drug. Prior medications are defined as those medications not concomitant, but taken within 30 days of screening Visit 1 (Day -14 to -1). Prior and concomitant medications will be summarized using the SAF. Medications will be tabulated for each

treatment arm using frequency counts and percentages. Subjects may have more than one medication per ATC text. At each level of subject summarization, a subject will be counted once if reporting one or more medications. Percentages will be based on the number of subjects in each treatment arm. The ATC Classes and preferred names within an ATC Class will be ordered by descending frequency based on all subjects.

Summaries will be generated separately for prior and concomitant medications, with ocular and non-ocular data also summarized separately using the SAF. Subject listings will group prior and concomitant medications together, with ocular and non-ocular information presented separately.

12. Efficacy Analyses

The primary efficacy and key secondary efficacy analyses are described in [Section 12.1](#). Sensitivity analyses on the primary and key secondary efficacy endpoints are described in [Section 12.2](#), and will be performed using the FAS.

12.1 Primary and Key Secondary Efficacy Analysis

The primary efficacy endpoint in this study is the percentage of subjects with a ≥ 3 -line (15-letter) gain, from baseline, in best distance-corrected visual acuity (BDCVA) at 40 cm (Precision Vision chart) and no loss in BDCVA ≥ 5 letters (ETDRS chart) at Visit 3, 1 hour following Dose 1 in the study eye. The key secondary efficacy endpoints are defined the same as the primary efficacy endpoint, except for being measured at 2 hours following Dose 1, 1 hour following Dose 2, and 2 hours following Dose 2, all at Visit 3.

The primary and key secondary efficacy analysis will be conducted in the FAS with missing data handled in the following manners:

1. Discontinuation of study drug and non-optimal compliance will be ignored [treatment policy strategy].
2. Withdrawal due to lack of efficacy or AEs: missing data will be singly imputed as failure [hypothetical strategy].
3. Missing data without withdrawal or withdrawal due to reasons other than lack of efficacy or AEs: missing data will be imputed employing Multiple Imputation (MI) using randomized treatment-based Markov Chain Monte Carlo (MCMC) methods.

No subject data will be excluded from the FAS due to protocol violations/deviations. The multiple imputation of missing values will be completed for the continuous measures (BDCVA at 40 cm and BDCVA at 4 m), then the response variable will be determined therefrom. Imputation of failure due to lack of efficacy or AE will be assigned after multiple imputation is performed.

Variables for treatment group, baseline for BDCVA at 40 cm and baseline for BDCVA at 4 m will also be included in the multiple imputation model. 25 complete imputed datasets will be created.

Example SAS® code for the multiple imputation:

```
PROC MI DATA=DATAIN OUT=MI NIMPUTE=25 SEED=118787 minimum=-0.3 maximum=1;
  MCMC INITIAL=EM;
  VAR TRTPN VA40 VA40BL VA4 VA4BL;
RUN;
```

Where TRTPN = treatment group, coded 1 for CSF-1, else 0

VA40 = value of BDCVA at 40 cm for Visit 3, 1 hour after Dose 1

VA40BL = baseline value of BDCVA at 40 cm

VA4 = value of BDCVA at 4 m for Visit 3, 1 hour after Dose 1

VA4BL = baseline value of BDCVA at 4 m

For each imputed dataset, a logistic regression model with baseline BDCVA at 40 cm as a covariate and treatment as a main effect will be used to obtain the treatment effect estimate, odds ratio, and 95% confidence interval (CI) for odds ratio.

Example SAS® code for the logistic model is shown here:

```
PROC LOGISTIC DATA=MI DESCENDING OUTTEST=PARMS COVOUT;
  BY _IMPUTATION_;
  CLASS TRTP;
  MODEL AVALC = BASE TRTP;
RUN;
```

where

- TRTP is the treatment arm (CSF-1, Vehicle);
- BASE is the baseline of BDCVA (letters) at 40 cm in the study eye;
- AVALC is the indicator for efficacy variable (Y, N).

SAS® PROC MIANALYZE will be used to obtain the overall p-value, odds ratio, and 95% confidence interval (CI) for odds ratio.

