### 5.3 Withdrawal Criteria

A subject may withdraw consent to participate in the study at any time for any reason. Subjects will be withdrawn from the study if any of the following criteria are met:

- Be a female of childbearing potential who is currently pregnant, nursing, or planning a pregnancy; tests positive to a urine pregnancy test at Visit 4; or refuses to use an adequate method of contraception for the duration of the study;
- Have an active ocular infection (bacterial, viral, or fungal), active ocular inflammation (e.g., moderate to severe blepharitis, allergic conjunctivitis, peripheral ulcerative keratitis, scleritis, uveitis) at Visit 2, Visit 3, or Visit 4 in either eye.
- Subjects may also be withdrawn from the study for the following reasons:
  - Adverse Event (AE)
  - Lost to follow-up
  - Death
  - Subject not adequately following required study procedures
  - Study terminated by the Sponsor
  - Other

Subject withdrawals will be documented on the subjects' source document.

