All reported study data will be recorded on the eCRFs supplied by Statistics & Data Corporation (SDC) using iMedNet™. Only the Principal Investigator and authorized study staff according to the Delegation of Responsibilities log are entitled to make entries in the eCRF. After data are entered into the clinical study database, electronic edit checks, and data review will be performed. All data validation specifications and procedures are detailed in the Data Validation Manual as a separate document. When the database has been declared to be complete and accurate, the database will be locked. Any changes to the database after data have been locked can only be made with the approval of the sponsor and [REDACTED] in consultation with SDC.

The final analyses outlined in this document will be carried out only after the following have occurred:

- All data management requirements are met according to SDC standard operating procedures, including data entry, performance of edit and validation checks, documentation and resolution of data queries, and database lock with written authorization provided by appropriate SDC and sponsor personnel.

- Protocol deviations have been identified and status defined (major/minor deviations), and completed prior to database lock and study unmasking.
- Analysis populations have been determined, and completed prior to database lock and study unmasking.
- Randomized treatment codes have been unmasked.

7. Analysis Sets

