8.2 Missing Data Handling and Sensitivity Analysis

The primary efficacy analysis and the key secondary analyses will be performed on the FAS, as described in section 12.1. In the event of missing data, the primary imputation method will be Multiple Imputation (MI), using randomized treatment-based Markov Chain Monte Carlo (MCMC). Sensitivity analyses will also be performed on the primary and key secondary efficacy endpoints measured at Visit 3 (Day 8). These sensitivity analyses will be considered supportive of the primary and key secondary analyses.

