8.4 Data Analysis Conventions

All data analysis will be performed by SDC after the study is completed and the database has been locked and released for unmasking. Statistical programming and analyses will be performed using SAS® Version 9.4 or higher. Output will be provided in rich text format for tables and portable document format for tables, listings, and figures using landscape orientation. All study data will be listed by subject, treatment, and visit (as applicable) based on all randomized subjects unless otherwise specified.

Summaries for continuous and ordinal variables will include the number of observations, arithmetic mean, standard deviation (SD), median, minimum, and maximum. Minima and maxima will be reported with the same precision as the raw values; means and medians will be presented to 1 additional decimal place than reported in the raw values. Standard deviations will be presented to 2 additional decimal places than reported in the raw values. Summaries for discrete variables will include frequency counts and percentages. All percentages will be rounded to 1 decimal place (i.e., XX.X%). Change from baseline will be calculated as baseline subtracted from the relevant post-baseline visit (Post-Baseline Visit – Baseline Visit), with baseline defined in Section 8.3 of this SAP.

Gains or improvements in BDCVA at 40 cm (Precision Vision chart) of \geq 3-lines (15-letters) are defined as changes from baseline in BDCVA at 40 cm (Precision Vision chart) of \leq -0.30 logMAR (e.g., -0.30, -0.32, ... logMAR).

Gains or improvements in BDCVA at 40 cm (Precision Vision chart) of \geq 2-line (10-letters) are defined as changes from baseline in BDCVA at 40 cm (Precision Vision chart) of \leq -0.20 logMAR (e.g., -0.20, -0.22, ... logMAR).

[figure not shown]
Similarly, loss in BDCVA of \geq 5 letters (ETDRS at 4 m) are defined as changes from baseline in BDCVA (ETDRS at 4 m) of \geq 0.10 logMAR (e.g., 0.10, 0.12, ... logMAR).

All statistical tests, unless otherwise indicated, will be 2-sided with a significance level of 0.05 ($\alpha = 0.05$). Confidence intervals (CI) for differences between treatment groups will be 2-sided at 95% confidence. All p-values will be rounded to 4 decimal places; p-values less than 0.0001 will be presented as " <0.0001 "; p-values greater than 0.9999 will be presented as " >0.9999 ." Unless otherwise specified, summaries will be presented by treatment group and, where appropriate, visit.

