8.5 Adjustment for Multiplicity

If the primary null hypothesis, H_{01} , is rejected at a 2-sided alpha = 0.05 in favor of CSF-1 in the alternative hypothesis, H_{11} , tested as delineated in the primary efficacy analysis section ([Section 12.1](#)), then the study will be considered a success and the following key secondary hypotheses will be tested in hierarchical order, each at a 2-sided alpha = 0.05, where inference will be made on each null hypothesis only if the prior null hypotheses are rejected in favor of CSF-1.

1. Visit 3 (Day 8), 2 hours following Dose 1 (H_{02})
2. Visit 3 (Day 8), 1 hour following Dose 2 (H_{03})
3. Visit 3 (Day 8), 2 hours following Dose 2 (H_{04})

9. Disposition of Subjects

Subject disposition will be presented in terms of the numbers and percentages of subjects who were randomized, completed the study, and discontinued from the study. A discontinued subject is someone who does not complete the 4 protocol-defined study visits. Subjects who are not discontinued from the study will be considered study completers. Disposition will be summarized by treatment arm for all randomized subjects. The reasons for study discontinuation will also be summarized and include: AE, lost to follow-up, physician decision, protocol violation, study terminated by sponsor, withdrawal by subject, death, and other. A subject listing will be provided which includes the date and reason for study discontinuation.

The number of subjects in each of the analysis sets (FAS, PPS, and SAF) will be displayed by treatment arm, with the number of subjects and percentages calculated using randomized subjects as the denominator. The number and percentage of subjects with any (major, or minor) protocol deviations will be summarized by treatment arm and overall for all randomized subjects. Protocol deviations will be classified as major or minor prior to the closure of the database during a masked review of each protocol deviation. Major deviations will be defined as those deviations that potentially affect the analysis of the primary study endpoint.

A subject listing will be provided which includes the date of the deviation, the deviation code and description, and the classification of whether the deviation was deemed major or minor. In addition, subject listings will include treatment arm and ICF signature date, and exclusions from the PPS. There will also be a listing of screen failures.

10. Demographic and Baseline Characteristics

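### Does the failure-imputation rule for withdrawal due to lack of efficacy need a listed reason and a stated time of classification?

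*SAP*

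**What the plan says.** SAP 12.1 sets three rules for missing data in the primary and key secondary analyses. Rule 1 ignores stopping of study drug and poor compliance. Rule 2 reads "Withdrawal due to lack of efficacy or AEs: missing data will be singly imputed as failure [hypothetical strategy". Rule 3 sends everything else to MI: values missing without withdrawal, and withdrawals for any other reason. On programming order, "Imputation of failure due to lack of efficacy or AE will be assigned after multiple imputation is performed". SAP 8.2 gives the general default: "In the event of missing data, the primary imputation method will be Multiple Imputation (MI), using randomized treatment-based Markov Chain Monte Carlo (MCMC".

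SAP 9 lists the discontinuation reasons to be summarised: "AE, lost to follow-up, physician decision, protocol violation, study terminated by sponsor, withdrawal by subject, death, and other". It also promises a subject listing with date and reason. Protocol 5.3 has its own list, introduced by "Subjects may also be withdrawn from the study for the following reasons", which names AE, loss to follow-up, death, inadequate adherence to procedures, termination by the sponsor, and other. Neither list names lack of efficacy.

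SAP 6 states what must precede the final analyses. Data entry, query resolution and authorised database lock come first. Then: "Protocol deviations have been identified and status defined (major/minor deviations), and completed prior to database lock and study unmasking" and "Analysis populations have been determined, and completed prior to database lock and study unmasking". Unmasking of the treatment codes is the last item. SAP 8.4 adds: "All data analysis will be performed by SDC after the study is completed and the database has been locked and released for unmasking". SAP 4.2 keeps subjects, investigators, site staff and sponsor masked for the whole study, apart from documented medical unmasking.

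**The concern.** The withdrawal reason decides the value analysed. Under rule 2 a missing subject counts as 0. Under rule 3 the same subject counts, on average, as roughly the arm's response rate. Half of the rule 2 trigger (AE) has a category on both lists. The other half (lack of efficacy) has none in the visible text, so such cases must be found by reading what was written under headings such as withdrawal by subject, physician decision or other.

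That reading is a judgement, and no passage says when it is made. SAP 6 names deviations and analysis populations as the items settled before unmasking. The masked review in SAP 9 covers protocol deviations. Failure is assigned after MI, and analysis follows release for unmasking. Taken together, these could let someone who knows the treatment codes decide which withdrawals count as failures in the primary test.

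There is also a labelling point. Setting an outcome to failure because of an intercurrent event is a composite strategy, yet rule 2 is tagged hypothetical. Protocol 10.10 puts the same tag on MI.

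**Working it through.** **Inputs.** From SAP 5: 140 per arm for power, about 150 per arm randomised, about 5% discontinuation, 42.5% v 17.5%, two-sided 0.05, Pearson chi-squared. Assumptions: k unclear withdrawals per arm with missing Visit 3 data (k = 1, 2, 4); MI credits each such subject with the arm's rate; baseline acuity is ignored. The documents give no value for k.

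**The plan's own figure.** With n = 140, the pooled standard error is sqrt(0.30 × 0.70 × 2/140) = 0.0548. The unpooled one is sqrt(0.425 × 0.575/140 + 0.175 × 0.825/140) = 0.0527. Power = Φ[(0.25 − 1.96 × 0.0548)/0.0527] = Φ(2.71) = 99.66%, which satisfies the stated >97.5%. Allowing for discontinuation, 140/0.95 = 147.4, so 148, consistent with about 150.

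**One subject.** Moving one subject from failure to MI raises CSF-1 by 100 × 0.425/150 = 0.283 points, or Vehicle by 100 × 0.175/150 = 0.117 points.

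**One reading applied to both arms.** The difference moves by 100 × k × (0.425 − 0.175)/150 = 0.167k points.

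**Opposite readings in the two arms.** The gap between the least and most favourable classification is 100 × k × (0.425 + 0.175)/150 = 0.4k points.

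| k per arm | Same reading: shift | Opposite readings: range of the difference | Gap |
|---|---|---|---|
| 1 | 0.17 | 24.72 to 25.12 | 0.4 |
| 2 | 0.33 | 24.43 to 25.23 | 0.8 |
| 4 | 0.67 | 23.87 to 25.47 | 1.6 |

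For k = 4, z lies between 4.54 and 4.82 under opposite readings, so p < 0.0001 throughout.

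**All discontinuations affected.** At 5% missing (7.5 per arm), MI for all gives 25.0 points. Failure for all gives 40.4% v 16.6%, or 23.8 points. The two mixed cases give 22.9 and 25.9 points. Power with 150 per arm is 99.4% or more in all four. Fewer subjects are likely to matter in practice, because the endpoint is at Day 8 and 5% is the whole-study rate.

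**At the edge of significance.** With Vehicle at 17.5% and 150 per arm, the smallest significant difference is 9.41 points (26.9% v 17.5%). Starting there with MI for all (p = 0.050), reading four per arm as failures in both arms gives p = 0.054. Opposite readings span 0.047 to 0.054 (k = 1), 0.044 to 0.059 (k = 2) and 0.039 to 0.069 (k = 4).

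**When the reason is fixed.** The reason is entered by masked staff (SAP 4.2), queried and locked (SAP 6, first item), and changeable after lock only with sponsor approval. Only then are the codes released. The sentence on assigning failure after MI describes programming order: MI fills the acuity values, then failure overwrites those flagged. It does not say when the flag is set. What remains open is how an ambiguous entry in a locked field is read.

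**The case for a change.** The strongest opposing case is that locking the entry does not lock its interpretation. If the text says only that the subject withdrew consent because the drops were not helping, somebody must decide whether that is lack of efficacy, and the SAP neither names that person nor requires the decision under masking. The sensitivity analyses are supportive; success rests on the primary test, which should be reproducible from its own text. Recording the step would cost about two lines.

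Part of this stands. Lack of efficacy has no visible category, SAP 6 does not name the classification, and the label on rule 2 is wrong. Three things limit the weight. First, rule 3 is residual, so a case not identified as lack of efficacy has a defined treatment, MI. Second, both lists end in other, and Protocol 5.3 lets a subject withdraw for any reason, so such a withdrawal has a place to be recorded. The eCRF is not among the documents and may hold a more specific code. Third, the larger swing (0.4k points) needs ambiguous CSF-1 and Vehicle cases to be read in opposite directions. Nothing in the documents suggests this, and masked recording works against it.

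On the label, the instruction itself is explicit: the value is failure. The SAP has already dropped the tag from rule 3, and SAP 1 says its methods supersede the protocol's.

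**Conclusion.** No change is needed. This is a small gap that analysts fill sensibly by reading the recorded reason in a locked database, together with a naming slip. Following the plan as written gives a sound primary result. At the planning rates the effect is about 0.17 points per unclear withdrawal per arm if both arms are read alike, and at most 0.4 points if they are read in opposite directions; p < 0.0001 in every case for k up to 4. Classification could tip the test only if the result fell close to the 9.41-point limit, and SAP 12.2 would expose that. Its all-missing-as-failure and observed-data analyses need no reason category. Its tipping-point analysis starts from the least favourable assignment, with all missing CSF-1 values as failures and all missing Vehicle values as successes, so significance there would cover any reading of the reasons.

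This rests on the planning rates, on MI crediting roughly the arm rate, and on k being small, as the 5% discontinuation rate and the Day 8 endpoint suggest. Noting in the masked pre-lock review which rule each withdrawal falls under, and calling rule 2 composite, would be tidy documentation. Neither would alter an imputation method, the sample size or a planned analysis.

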#### Methods for Assignment to Treatment Groups

Each subject who signs an ICF will be assigned a subject number. Subject numbers will be assigned in sequential order beginning with 001. Once a subject meets all qualification criteria at Visit 2, he/she will be randomized in a 1:1 ratio via an Interactive Response Technology (IRT) system to one of the following treatment groups: 1: CSF-1 (pilocarpine hydrochloride 0.4% ophthalmic solution), 2: Vehicle, and stratified by iris color (brown versus light [i.e., blue, green, gray, and hazel]) and by baseline manifest refraction spherical equivalent (-4.5 D to <-0.5 D, -0.5 D to +0.75 D, and >+0.75 D to +2.0 D); randomization will not be stratified by site.

At least approximately 30% of subjects will have light (i.e., blue, green, gray, and hazel) iris and at least approximately 30% will have a brown iris. The actual percentages will vary based on enrollment.

Randomization will be used to avoid bias in the assignment of subjects to treatment, to increase the likelihood that known and unknown subject attributes (e.g., iris color and baseline characteristics) are evenly balanced across treatment groups, and to enhance the validity of statistical comparisons across treatment groups. Double-masked treatment will be used to reduce the potential of bias during data collection and the evaluation of clinical endpoints.

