4.1 Method of Assigning Subjects to Treatment Groups

Each subject who signs an informed consent form (ICF) will be assigned a subject number. Subject numbers will be assigned in sequential order beginning with 001. Once a subject meets all qualification criteria at Visit 2 (Day 1), they will be randomized in a 1:1 ratio via an Interactive Response Technology (IRT) system to one of the following treatment groups: (1) CSF-1 or (2) Vehicle, and stratified by iris color (brown versus light [i.e., blue, green, gray, and hazel]) and by baseline manifest refraction spherical equivalent <-0.5 D, -0.5 D to +0.75 D, and >+0.75 D); randomization will not be stratified by site.

At least, approximately, 30% of subjects will have a light iris and at least, approximately, 30% will have a brown iris. The actual percentages will vary based on enrollment.

Randomization will be used to avoid bias in the assignment of subjects to treatment, to increase the likelihood that known and unknown subject attributes (e.g., iris color and baseline characteristics) are evenly balanced across treatment groups, and to enhance the validity of statistical comparisons across treatment groups. Double-masked treatment will be used to reduce the potential of bias during data collection and the evaluation of clinical endpoints.

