10.1 Demographics

Subject demographic data collected in this study, age, sex, race, ethnicity, and childbearing potential. Subjects who record more than one race will be grouped into a single category denoted as multi-racial, and subjects who record more than one iris color (study eye) will be classified as heterochromia. Sex, race, ethnicity, childbearing potential, and iris color will be presented using descriptive summary statistics with frequency counts and percentages. Age (years) will be summarized with continuous descriptive statistics. Categorical variables will be summarized with number and percentage.

Demographic variables along with two baseline characteristics, iris color of study eye and manifest refraction spherical equivalent (MRSE), will be summarized for the FAS and PPS by treatment arm and overall in tables. A subject listing that includes all summarized demographic and baseline variables will also be provided.

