12.2 Sensitivity Analysis for Primary and Key Secondary Efficacy Endpoints

Sensitivity Analysis for the primary and key secondary efficacy endpoints include:

1. All missing data imputed as failure using the FAS
2. Observed data only using the FAS

3. Observed data only using the PPS
4. Missing data will be imputed employing tipping point approach. The analysis will be based on the FAS

For #1, #2 and #3 sensitivity analyses, the analysis of primary and key secondary efficacy endpoints will be performed using a logistic regression model with baseline BDCVA at 40 cm as a covariate and treatment as a main effect. The odds ratio, and 95% confidence interval (CI) for odds ratio will be provided. p-values will be presented for the main effect of treatment group using a Wald statistic.

Tipping Point Analysis of Primary and Key Secondary Efficacy Variables

[figure not shown]
Missing primary and key secondary efficacy endpoint values (i.e., binary response values) will be imputed using tipping point approach. First set all records in CSF-1 with missing value as failures and all records in Vehicle with missing value as successes, that is the worst case. The imputed data will be analyzed using a logistic regression model with baseline BDCVA at 40 cm as a covariate and treatment as a main effect. The p-value, odds ratio, and 95% confidence interval (CI) for odds ratio will be provided. If the p-value is less or equal to 0.05 for the worst case, then stop there. If the p-value is greater than 0.05 for the worst case, then set the missing records as failures or successes in all possible combinations from worse case to the best case until the p-value turns from >0.05 to ≤ 0.05 .

13. Exploratory Analysis

28FEB2022

Confidential & Proprietary

Page 32 of 43

14. Safety Analyses

All safety analyses will be conducted using the SAF. In addition to AEs, BCVA at distance under normal and low-luminance testing conditions, findings from slit-lamp biomicroscopy examination, conjunctival redness grading, study drug drop comfort assessment, dilated indirect fundoscopy, and IOP measurements will be summarized descriptively using quantitative and qualitative summary statistics by treatment arm and subject visit, as appropriate. All such measurements related to safety endpoints will also be presented in a detailed subject listing.

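### Randomisation is stratified by iris colour and refraction, but no readable efficacy model in SAP 12.1–12.2 includes either factor: a modest, conditional loss of efficiency, not a threat to a positive result

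*SAP*

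**What the plan says.** SAP 4.1 has subjects randomised 1:1, "stratified by iris color (brown versus light [i.e., blue, green, gray, and hazel]) and by baseline manifest refraction spherical equivalent". The protocol, under Methods for Assignment to Treatment Groups, gives the refraction groups with outer limits: "by baseline manifest refraction spherical equivalent (-4.5 D to <-0.5 D, -0.5 D to +0.75 D, and >+0.75 D to +2.0 D". The cut-points agree, so there are 2 × 3 = 6 strata.

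The analysis model in SAP 12.1 has two terms: "a logistic regression model with baseline BDCVA at 40 cm as a covariate and treatment as a main effect will be used". The example code agrees: "MODEL AVALC = BASE TRTP". In SAP 12.2, the first three sensitivity analyses and the tipping-point analysis use the same "logistic regression model with baseline BDCVA at 40 cm as a covariate and treatment as a main effect". The imputation step lists "VAR TRTPN VA40 VA40BL VA4 VA4BL", again with neither factor.

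Both factors are available. SAP 10.1 states that "two baseline characteristics, iris color of study eye and manifest refraction spherical equivalent (MRSE), will be summarized". The readable protocol models (synopsis and section 10.7) name neither factor either, and the readable SAP gives no reason for leaving them out. The content of SAP 13 and 16 is not visible, so this point is confined to SAP 12.1–12.2.

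**The concern.** Stratified randomisation forces the arms to be balanced on the strata. If the strata predict response, that balance reduces the true sampling variability of the treatment estimate. A model without the strata does not see the reduction, so its standard error can be too large. The test then rejects less often than 5% under the null and gives up some power. If a factor only modifies the drug response and is not prognostic on vehicle, there is no conservatism under the null.

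The sponsor evidently thought both factors mattered: it stratified on them and set approximate 30% minimums for each iris group.

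What is at stake is power for the smaller effects, not the validity of a positive finding. The readable power statement covers 1 hour after each dose. The tests run in a fixed order: H01, H02 (2 hours after Dose 1), H03 (1 hour after Dose 2), H04 (2 hours after Dose 2). One failure ends inference. If the 2-hour effects are smaller than planned, lost efficiency at H02 also blocks H03 and H04.

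**Working it through.** **Inputs from the documents.** 140 per arm, 42.5% versus 17.5%, Pearson chi-squared, two-sided 0.05, about 5% discontinuation (SAP 5); 1:1 allocation in six strata (SAP 4.1).

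**Stated power.** The pooled rate is 0.30.
- Null SE = √(0.30 × 0.70 × 2/140) = 0.0548.
- Alternative SE = √[(0.425 × 0.575 + 0.175 × 0.825)/140] = 0.0527.
- Power = Φ[(0.25 − 1.96 × 0.0548)/0.0527] = Φ(2.71) = 99.66%, consistent with the stated bound of more than 97.5%.
- 140/0.95 = 147.4, rounded up to 148, consistent with about 150 per arm.

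**Main simulation.** 280 subjects, with logistic Wald tests with and without the strata. Assumptions that are not in the documents: permuted blocks of 4 within strata, 45% in one iris group, refraction split 30/45/25%, and a baseline log-odds ratio of 0.4 per SD. Strata strength is the log-odds ratio for iris / per refraction step. The three non-null settings correspond to odds ratios of about 1.65/1.35, 2.2/1.8 and 3.3/2.7. There were 20,000 replicates per null setting (Monte Carlo SE about 0.15 points) and 10,000 per power setting (SE up to 0.45 points).

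| Strata strength | Type I error, SAP model | Type I error, adjusted | Power at 30% vs 17.5%, SAP → adjusted |
|---|---|---|---|
| 0/0 | 4.7–4.9% | 4.9–5.1% | 71.0 → 71.2% |
| 0.5/0.3 | 4.7–4.8% | 5.1–5.2% | 70.9 → 71.7% |
| 0.8/0.6 | 4.4% | 4.9–5.2% | 70.9 → 73.1% |
| 1.2/1.0 | 3.6–3.8% | 5.2–5.3% | 71.6 → 76.6% |

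Type I error ranges cover control rates of 17.5% and 30%. Further results:
- **Robustness.** With baseline acuity correlated 0.4 with refraction, type I error is 4.2% versus 4.9% (0.8/0.6) and 3.8% versus 4.9% (1.2/1.0). With a sparse 15/80/5% refraction split it is 4.3% versus 4.7% (0.8/0.6).
- **Other effects.** At 35% versus 17.5%, adjustment gains 0.4, 1.0 and 1.7 points for the three non-null settings. At 42.5% versus 17.5%, both models have at least 99.8% power.
- **Both 2-hour tests significant** at 30% versus 17.5%, with an assumed within-subject latent correlation of 0.6: 54.6 → 55.7%, 54.9 → 58.1% and 55.9 → 62.9%.
- **Reported odds ratio** at 42.5% versus 17.5% (median): 3.66 → 3.82, 3.66 → 4.08 and 3.62 → 4.60.

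**Second simulation.** This used 50/50 iris colour, a baseline odds ratio of 1.3 per SD, and strata odds ratios of 1/1, 1.5/1.3, 2/1.5, 3/2 and 4/3. There were 6,000 null runs (SE about 0.3 points) and 3,000 runs per alternative.
- Null rejection by the SAP model at 30% in both arms was 5.2, 4.7, 4.8, 3.4 and 3.2%. The adjusted model stayed at 4.7–5.5%.
- The standard errors show the mechanism. At 3/2, the SAP model's mean SE is 0.2649 against an actual sampling SD of 0.2498, a ratio of 1.060. The effective critical value is therefore 1.96 × 1.060 = 2.08, which implies a two-sided error of about 3.8%, close to the simulated 3.4%. The adjusted model's SE and SD agree (0.2817 and 0.2823).
- Relative efficiency at the design rates is the squared ratio of mean z (SAP/adjusted): 0.99 with non-prognostic strata, then 0.98, 0.96, 0.92 and 0.87. For 3/2: ln(3.598)/0.2863 = 4.47 and ln(4.221)/0.3084 = 4.67, so (4.47/4.67)² ≈ 0.92.
- Power at 33% versus 17.5% went from 85.8 to 86.3% with non-prognostic strata, then 85.1 to 86.0, 85.4 to 86.3, 86.4 to 88.5 and 88.3 to 91.9%.

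**Imputation.** 300 subjects, 5% missing at random, 25 imputations, 1,200 replicates, 30% versus 17.5%, strata-adjusted analysis. Mean treatment log-odds ratio with complete data / imputation without strata / imputation with strata was 0.789 / 0.785 / 0.789 at 0.8/0.6 and 0.851 / 0.837 / 0.852 at 1.2/1.0. Leaving the strata out attenuates the estimate by about 0.5% (0.004/0.789) to 2% (0.014/0.851).

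**The case against.** The strongest reply is that this is a consistent, pre-specified choice that does no harm. The protocol omits the strata too, type I error is never inflated, and the planned effect is detected almost surely either way. Larger gains need strong strata: at 1.2/1.0 the odds ratio across the refraction range is about 7.4 (e²), and nothing in the documents supports that. At 0.5/0.3 the gain is 0.8 points, of which 0.2 appears even when the strata are irrelevant. This stands, and it is why the point is rated as modest.

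The standard error argument also needs care. At 30% versus 17.5%, the SAP model's mean SE against its actual SD was 0.298 versus 0.299 at 0.5/0.3, so correct, and 0.297 versus 0.288 at 0.8/0.6, about 3% too large. Adjustment does not shrink the SE of the log-odds ratio; it raises it, to 0.303, 0.310 and 0.324 across the three settings. Power rises because the conditional log-odds ratio grows by more. The hypotheses are stated as differences in percentages, so a larger odds ratio must not be read as a larger drug effect. This also stands and is dealt with in the fix.

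The 2-hour rates are assumed, and redacted text after the power statement may contain others. The joint 2-hour figure leaves out H03, so it is not the probability of completing the sequence. None of this removes the mismatch between design and analysis, or supplies a reason for it.

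**Conclusion.** The concern holds. Every readable model in SAP 12.1–12.2, and the imputation model, ignores the two factors that define the randomisation. The consequence is a conservative or neutral test. Efficiency loss is about 2–8% for mild to strong strata and 13% in the extreme case. The power cost is negligible at 42.5% versus 17.5%, and about 1 to 5 points at an assumed 30% versus 17.5% when the strata are prognostic. A positive result from the current model would not be undermined.

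The size rests on the assumed strata effects, stratum shares and block size, and on assumed 2-hour response rates, none of which the readable documents give. If the strata do not predict response beyond baseline acuity, essentially nothing is lost. The change is still worth making, because it is nearly free and protects the later tests in the sequence.

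**What to change.** Before unmasking, amend SAP 12.1–12.2 as follows.

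1. Add iris colour and refraction group as class effects to the primary, key secondary, sensitivity and tipping-point models. Keep the current two-term model as supportive.
2. Take both factors as randomised in the IRT. SAP 10.1 says that "subjects who record more than one iris color (study eye) will be classified as heterochromia", which is not a randomisation level, so the demographic iris variable should not be used.
3. Add 0/1 indicators for iris and for two refraction groups to the imputation variables, in the way treatment is already handled.
4. State that the odds ratio is conditional on baseline acuity and the strata. Also report a standardised difference in proportions with a 95% CI. Protocol 10.7 already promises marginal proportions and their difference.
5. Pre-specify a collapsing rule, since no minimum size is set for refraction groups. For example, merge an outer group into the middle one if it has fewer than 5 responders or 5 non-responders in the masked, pooled, observed data for the primary endpoint, and apply the same grouping to all four endpoints.

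The cost is SAP wording, example code and 3 degrees of freedom; no new data are needed. The downside is an odds ratio that is numerically larger than under the current model without any change in drug effect. If the sponsor prefers the current model, the minimum is a stated reason plus a strata-adjusted sensitivity analysis. If the data are already unmasked, the adjusted model can only be supportive.
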